2.8.3.8.1. Time Period and Frequency for Collecting AE and SAE Information

All SAEs, AESI, MAAE, and AEs leading to discontinuation from study participation will be collected from the start of study intervention dosing until Day 181 (Month 6)/EoS or withdrawal from the study at the timepoints specified in the SoA (Section 5.3).

All solicited local and systemic ARs will be collected from the start of study intervention and during the 7 days following the study intervention (ie, the day of study intervention dosing and 6 subsequent days).

All unsolicited AEs will be collected from the start of study intervention and during the 28 days following the study intervention (ie, the day of study intervention and 27 subsequent days).

Medical occurrences that begin before the start of study intervention but after obtaining informed consent will be recorded as medical history/current medical conditions, not as AEs; however, if the condition worsens at any time after study intervention administration, it will be recorded and reported as an AE.

All SAEs will be recorded and reported to the Sponsor or designee immediately and under no circumstance should this exceed 24 hours of becoming aware of the event, as indicated in Section 5.3. The Investigator will submit any updated SAE data to the Sponsor within 24 hours of it being available.

Investigators are not obligated to actively seek information on AEs or SAEs after the study completion Visit. However, if the Investigator learns of any SAE, including a death, at any time after a participant has been discharged from the study, and the Investigator considers the event to be reasonably related to the study intervention or study participation, the Investigator must promptly notify the Sponsor.

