2.8.3.9. Solicited Adverse Reactions

Solicited ARs are a subset of AEs consisting of selected signs and symptoms that participants are asked to record/report. In this study, the solicited ARs are reactogenicity events. The term "reactogenicity" refers to the occurrence of transient adverse effects associated with study intervention dosing. The eDiary will solicit daily participant reporting of ARs using a structured

checklist. Participants will record such occurrences in the eDiary on the day of study intervention dosing and 6 subsequent days.

Severity grading of reactogenicity will occur automatically based on participant entry into the eDiary according to the grading scales presented Section 5.3, which are modified from the Toxicity Grading Scales for Healthy Adult and Adolescent Volunteers Enrolled in Preventive Vaccine Clinical Trials (DHHS 2007b). All solicited ARs (local and systemic) will be considered causally related to dosing.

If a participant reports a solicited AR with onset during the solicited period, but they did not record the event in the eDiary, then the event should be recorded by study staff in EDC.

If the event starts during the solicited period, but continues beyond 7 days after dosing, the participants should notify the site to provide an end date and close out the event in EDC, where reactogenicity is collected.

If the participant reported an event that started after the solicited period (ie, beyond 7 days after dosing), it should be recorded as an AE in EDC. Causality for these events will be determined per assessment by the Investigator.

Any solicited AR that meets any of the following criteria must be entered into the participant's source document and must also be recorded by the clinic staff in EDC, where reactogenicity is collected:

- Solicited local or systemic AR that results in a visit to a healthcare practitioner (medically attended AE).
- Solicited local or systemic AR lasting beyond 7 days poststudy intervention dosing.
- Solicited local or systemic AR that leads to participant discontinuation from study participation.
- Solicited local or systemic AR that otherwise meets the definition of an SAE.

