Injection site erythema (redness)	<25 mm/ <2.5 cm	25-50 mm/ 2.5-5 cm	51-100 mm/ 5.1-10 cm	>100 mm/ >10 cm	Necrosis or exfoliative dermatitis
Injection site swelling/induration (hardness)	<25 mm/ <2.5 cm	25-50 mm/ 2.5-5 cm	51-100 mm/ 5.1-10 cm	>100 mm/ >10 cm	Necrosis
Axillary (underarm) swelling or tenderness ipsilateral to the side of injection	None	No interference with activity	Some interference with activity	Prevents daily activity	Requires emergency room visit or hospitalization
Systemic	I				
Headache	None	No interference with activity	Some interference with activity	Prevents daily activity	Requires emergency room visit or hospitalization
Fatigue	None	No interference with activity	Some interference with activity	Prevents daily activity	Requires emergency room visit or hospitalization
Myalgia (muscle aches all over body)	None	No interference with activity	Some interference with activity	Prevents daily activity	Requires emergency room visit or hospitalization
Arthralgia (joint aches in several joints)	None	No interference with activity	Some interference with activity	Prevents daily activity	Requires emergency room visit or hospitalization

Reaction	Grade 0	Grade 1	Grade 2	Grade 3	Grade 4
	(None)	(Mild)	(Moderate)	(Severe)	(Life-threatening)
Nausea/vomiting	None	No interference with activity or 1-2 episodes/ 24 hours	Some interference with activity or >2 episodes/2 4 hours	Prevents daily activity, requires outpatient intravenous hydration	Requires emergency room visit or hospitalization for hypotensive shock
Chills	None	No interference with activity	Some interference with activity not requiring medical intervention	Prevents daily activity and requires medical intervention	Requires emergency room visit or hospitalization
Fever (oral)	<38.0°C	38.0-38.4°C	38.5-38.9°C	39.0-40.0°C	>40.0°C
	<100.4°F	100.4-101.1°F	101.2-102.0°F	102.1-104.0°F	>104.0°F

Note: Events listed above but starting >7 days poststudy intervention dosing will be recorded in the eCRF. Causality for each event will be determined per assessment by the Investigator.

Modified from the Toxicity Grading Scale for Healthy Adult and Adolescent Volunteers Enrolled in Preventive Vaccine Clinical Trials (DHHS 2007b).

Assessment of Causality

- The Investigator must assess the relationship between study intervention and each occurrence of each AE/SAE, based on clinical judgment, and document this in the source document and EDC.

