- Not related: There is not a reasonable possibility of a relationship to the study intervention. Participant did not receive the study intervention OR temporal sequence of the AE onset relative to administration of the study intervention is not reasonable OR the AE is more likely explained by another cause than the study intervention.
- **Related:** There is a reasonable possibility of a relationship to the study intervention. There is evidence of exposure to the study intervention. The temporal sequence of the AE onset relative to the administration of the study intervention is reasonable. The AE is more likely explained by the study intervention than by another cause.
- There may be situations in which the Investigator has minimal information concerning an AE; however, an assessment of causality must be provided by the Investigator at the time of reporting to the Sponsor or designee based on their clinical understanding of the event, knowledge of the study intervention, and current information available.

Follow-up of AEs and SAEs

The Investigator is obligated to perform or arrange for the conduct of supplemental measurements and/or evaluations as medically indicated or as requested by the Sponsor or

designee to elucidate the nature and/or causality of the AE or SAE as fully as possible. This may include additional laboratory tests or investigations, histopathological examinations, or consultation with other health care professionals.

If a participant dies during participation in the study or during a recognized follow-up period, the Investigator will provide the Sponsor or designee with a copy of any postmortem findings including histopathology.

New or updated information will be recorded as revisions to the original report.

The Investigator will report any updated SAE data to the Sponsor or designee within 24 hours of receipt of the information.

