2.5.5.2.2. Unsolicited AEs by SOC and PT

The following summary tables of TEAEs up to 28 days after vaccine injection will be provided by SOC and PT using frequency counts and percentages (i.e., number and percentage of participants with an event) and number of events:

- Any unsolicited TEAEs
- Any unsolicited treatment-related TEAEs
- Any serious TEAEs
- Any treatment-related serious TEAEs
- Any unsolicited severe TEAEs
- Any unsolicited treatment-related severe TEAEs
- Any unsolicited medically attended TEAEs
- Any unsolicited treatment-related medically attended TEAEs
- Any unsolicited treatment-emergent AESI
- Any unsolicited TEAEs leading to discontinuation from participation in the study

Unsolicited TEAEs and unsolicited treatment-related TEAEs will be summarized by SOC and PT for TEAEs with occurrence in \geq 1% of participants in any vaccination group based on PT, and also presented by SOC, PT, and severity using frequency counts and percentages.

Summary tables for all unsolicited SAEs, AESIs, MAAEs, AE leading to discontinuation from the study, and TEAE leading to death through Day 181/EoS will also be provided by SOC and PT as applicable.

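### For unsolicited adverse events the protocol's causality rule sets two conflicting tests, so some events fit both categories and some neither, with under-attribution to the vaccine the likely direction

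*Protocol*

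**What the plan says.** Protocol 5.3.5 (Assessment of Causality) gives the investigator two categories and no third.

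- *Related* begins "There is a reasonable possibility of a relationship to the study intervention". It then asks for exposure and reasonable timing, and ends with "The AE is more likely explained by the study intervention than by another cause".
- *Not related* begins "There is not a reasonable possibility of a relationship to the study intervention". It then lists alternatives joined by OR: no exposure, unreasonable timing, and finally "OR the AE is more likely explained by another cause than the study intervention".

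The call is a matter of judgment for every event: "The Investigator must assess the relationship between study intervention and each occurrence of each AE/SAE, based on clinical judgment".

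Three other places bear on the point.

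- Protocol 2.8.3.9 takes solicited reactions out of the test: "All solicited ARs (local and systemic) will be considered causally related to dosing". The same symptoms starting after the solicited period go back to the investigator's causality assessment.
- Protocol 2.8.3.8.1, on SAEs learned of after a participant has left the study, triggers notification when "the Investigator considers the event to be reasonably related to the study intervention or study participation". It has no likelihood condition.
- SAP 2.5.5.2.1, 2.5.5.2.2 and 2.5.5.2.4 use the classification, for example in the table titled "Any unsolicited treatment-related TEAEs" and its serious, severe and medically attended counterparts. SAP 2.5.5 applies these analyses to all three parts.

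**The concern.** Reasonable possibility and more likely than not are different thresholds, and the rule states both without saying which governs. Two investigators who hold the same view of the same event can record different answers, each with support in the text. Because one OR clause is enough for *Not related* while *Related* appears to need all its sentences, the wording leans towards *Not related*.

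At stake is the meaning of the treatment-related TEAE and SAE tables. Protocol 2.8.3.8.4 requires reports on suspected unexpected serious adverse reactions, and the documents state no separate sponsor threshold for causality. The call may therefore also influence which SAEs are treated as suspected reactions. The protocol describes the risk of myocarditis or pericarditis after non-coronavirus mRNA vaccines as unknown (1.3.1). A case with a plausible alternative cause is the kind of event on which the two tests can disagree.

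**Working it through.** The plan has no figure on this point to reproduce, so the first step is a comparison of the text.

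**Step 1: apply both definitions to each kind of event.** Let p be the investigator's probability that the vaccine caused the event, with all alternatives taken together. Assume exposure occurred and timing is reasonable.

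| Investigator's view | *Related*: opening | *Related*: closing condition | *Not related*: opening | *Not related*: OR clause | Result |
|---|---|---|---|---|---|
| No reasonable possibility | fails | fails | met | met | Not related |
| Reasonable possibility, p < 0.5 | met | fails | fails | met | Conflict |
| p = 0.5 | met | fails | fails | fails | Neither likelihood clause met |
| p > 0.5 | met | met | fails | fails | Related |

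The first and last rows are clear. In the second row the opening test says related and the OR clause says not related. The third row has no defined home.

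**Step 2: scope.** Solicited reactions in the 7-day window never reach this test (Protocol 2.8.3.9). The affected events are unsolicited AEs and SAEs, and solicited-type symptoms that start after the window.

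**Step 3: illustration of the literal likelihood condition.** No event rates or relative risks (RR) are given, so those below are assumed. If vaccinated cases cannot be told apart from background, the share caused by the vaccine is (RR − 1)/RR:

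- RR 1.25: 0.25/1.25 = 0.20
- RR 1.5: 0.5/1.5 = 0.33
- RR 1.9: 0.9/1.9 = 0.47
- RR 2.0: 1.0/2.0 = 0.50
- RR 2.5: 1.5/2.5 = 0.60

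The share exceeds one half only when RR is above 2, whatever the background rate. With 1500 vaccinated (Protocol Tables 9 and 13), RR 1.5 and a 1% background, there are 1500 × 0.01 × 1.5 = 22.5 events, of which 1500 × 0.01 × 0.5 = 7.5 are vaccine-caused. Under this literal reading all fall under *Not related*. The vaccine-caused count is 3.8 at a 0.5% background and 37.5 at 5%.

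**Step 4: what the all-causality comparison still shows.** Those events remain in the tables by arm. At RR 1.5, with 1500 per arm and two-sided alpha 0.05, the power of that comparison is 0.14, 0.23 and 0.81 for backgrounds of 0.5%, 1% and 5%.

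**Step 5: how timing changes Step 3.** Assume 5% versus 9% over 28 days: 75 versus 135 events, an excess of 60, RR 1.8, and an overall share of 60/135 = 44%. Spread the background evenly.

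- If the whole excess falls in days 1–7, background there is 75 × 7/28 = 18.75, and 60/78.75 = 76% of cases in that week are vaccine-caused.
- If it falls in days 1–14, background is 75 × 14/28 = 37.5, and 60/97.5 = 62% are.

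An overall RR below 2 therefore does not prevent individual cases from passing the likelihood condition.

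**The case against.** The strongest reply is that little depends on the classification. AEs are documented whatever the suspected cause (Protocol 2.8.3.8.2). The SAP tabulates all TEAEs, including severe, serious, medically attended and AESI events, by arm irrespective of relatedness. No primary safety endpoint uses relatedness (Protocol Tables 2, 8 and 12). SAEs go to the sponsor within 24 hours and AESIs are reported the same way (Protocol 2.8.3.8.1 and 5.3.6). All of this stands and limits the effect to the related subset. The all-causality tables are only a partial safeguard, because their power for modest excesses of uncommon events is low (Step 4).

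A second reply is that the later sentences simply spell out what reasonable possibility means, so there is one test. The protocol does not say this. That reading would also turn reasonable possibility into more likely than not, and ties would still be unclassified.

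A third reply is that the post-discharge wording in 2.8.3.8.1 is a notification trigger and does not classify events for the tables. That is correct. It shows a different phrasing elsewhere, but the conflict within 5.3.5 does not depend on it.

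A reader might go further and infer that an event the vaccine less than doubles can never be called related, so that the related tables would show zero despite a real excess. The documents do not support this. Investigators judge each occurrence, with timing and clinical features available, and are blinded (Protocol 2.6.1); they do not apply an arm-level fraction. Step 5 shows that timing alone can reverse the result. Nor do the documents say that the investigator's call alone decides expedited reporting.

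**Conclusion.** The contradiction in Protocol 5.3.5 is real, and nothing elsewhere in the protocol or SAP resolves it. For unsolicited AEs and SAEs and late-onset solicited-type symptoms, the firm conclusion is inconsistent classification. Under-attribution is the likely direction, because the OR clause is sufficient alone, but it is not certain: an investigator may follow the opening sentence of *Related* instead.

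The number of events affected cannot be derived from the documents. The cut at RR 2 holds only for cases that neither timing nor clinical features separate from background, and the counts in Step 3 rest on assumed rates. The affected outputs are the treatment-related TEAE and SAE tables and, possibly, the handling of suspected serious reactions. No hypothesis, analysis set or primary endpoint changes. It should be corrected as an inconsistency in a safety definition; it does not threaten the trial's main conclusions.

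**What to change.** Reconcile 5.3.5 to the single test that already opens both definitions.

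- In *Related*, delete the sentence "The AE is more likely explained by the study intervention than by another cause" and leave reasonable possibility, exposure and reasonable timing.
- In *Not related*, replace the last OR clause so that an alternative cause is sufficient only when it rules the vaccine out, for example: *or another cause accounts for the event and leaves no reasonable possibility that the study intervention contributed*.
- Make the eCRF completion guidance match.
- For events already classified, state in the CSR which reading was used.

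The cost is two sentences in Appendix 3 plus the guidance. Somewhat more events would be classed as related in both arms, under blinded assessment, and there might be a few more expedited reports.

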5.3.6. Reporting of SAEs/AESI

Note: AESI will be reported in the same way as SAEs.

The primary mechanism for reporting an SAE to the Sponsor or designee will be the electronic EDC.

If the electronic system is unavailable, then the site will use the paper SAE data collection tool provided by the Sponsor to report the event within 24 hours.

- SAE reports should be emailed to [contact].
- The site will enter the SAE data into the electronic system as soon as it becomes available.

NOTE: Initial notification via email or fax does not replace the need for the Investigator to complete and sign the electronic SAE data collection tool within the designated reporting timeframes.

After the study is completed at a given site, the EDC tool will be taken offline to prevent the entry of new data or changes to existing data. If a site receives a report of a new SAE from a study participant or receives updated data on a previously reported SAE after the EDC tool has been taken offline, then the site can report this information on a paper SAE form (see next section).

5.4. Appendix 4: Adverse Event of Special Interest

Investigators should report all events that fall into the categories presented in Table 17 as an AESI per the reporting processes in Section 5.3.6. These AESIs are medical concepts that are generally of interest in vaccine safety surveillance as per the Brighton Collaboration and Safety Platform for Emergency Vaccines or the vaccine platform.

Medical Concept	Additional Notes
Thrombocytopenia	 Platelet counts <125 × 10⁹. Including but not limited to immune thrombocytopenia, platelet production decreased, thrombocytopenia, thrombocytopenic purpura, thrombotic thrombocytopenic purpura, or Hemolysis, elevated liver enzymes, low platelet count syndrome.
New onset of or worsening of the following neurologic diseases:	 Guillain-Barre Syndrome. Acute disseminated encephalomyelitis. Idiopathic peripheral facial nerve palsy (Bell's palsy). Seizures including but not limited to febrile seizures and/or generalized seizures/convulsions.
Anaphylaxis	 Anaphylaxis associated with study intervention dosing as defined per protocol (Section 2.8.3.11.1). Follow reporting procedures in Section 5.3.6.
Myocarditis/Pericarditis	 Myocarditis. Pericarditis. Myopericarditis.

Table 17:Adverse Events of Special Interest

5.5. Appendix 5: CDC Working Case Definitions of Pericarditis, Myocarditis, and Myopericarditis Occurring After Receipt of COVID-19 mRNA Vaccines

The CDC Working Case Definitions of probable and confirmed myocarditis, pericarditis, and myopericarditis (Gargano et al 2021) are provided in Table 18 as guidance.

Table 18:	Case Definitions of Probably and Confirmed Myocarditis, Pericarditis, and
	Myopericarditis

Condition	Definition	
Acute	Probable case	Confirmed case
myocarditis	Presence of ≥ 1 new or worsening of the following clinical symptoms:*	Presence of ≥ 1 new or worsening of the following clinical symptoms:*
	 Chest pain, pressure, or discomfort Dyspnea, shortness of breath, or 	 Chest pain, pressure, or discomfort Dyspnea, shortness of breath, or pain with breathing
	pain with breathingPalpitations	PalpitationsSyncope
	 Syncope OR, infants and children aged <12 years might instead have ≥2 of the following symptoms: Irritability Vomiting Poor feeding Tachypnea Lethargy 	 OR, infants and children aged <12 years might instead have ≥2 of the following symptoms: Irritability Vomiting Poor feeding Tachypnea Lethargy
	 AND ≥1 new finding of Troponin level above upper limit of normal (any type of troponin). Abnormal ECG or EKG or rhythm monitoring findings consistent with myocarditis[§]. Abnormal cardiac function or wall motion abnormalities on echocardiogram. cMRI findings consistent with myocarditis[¶]. 	 AND ≥1 new finding of Histopathologic confirmation of myocarditis[†]. cMRI findings consistent with myocarditis[¶] in the presence of troponin level above upper limit of normal (any type of troponin).

Condition	Definition		
	AND	AND	
	• No other identifiable cause of the symptoms and findings.	• No other identifiable cause of the symptoms and findings.	
Acute pericarditis**	 Presence of ≥2 new or worsening of the following clinical features: Acute chest pain^{††} Pericardial rub on exam New ST-elevation or PR-depression on EKG New or worsening pericardial effusion on echocardiogram or MRI 		
Myopericarditis	This term may be used for participants who meet criteria for both myocarditis and pericarditis.		

Abbreviations: cMRI = cardiac magnetic resonance imaging; ECG or EKG = electrocardiogram; MRI = magnetic resonance imaging.

* Persons who lack the listed symptoms but who meet other criteria may be classified as subclinical myocarditis (probable or confirmed).

[†] Using the Dallas criteria (Aretz et al 1987). Autopsy cases may be classified as confirmed clinical myocarditis on the basis of meeting histopathologic criteria if no other identifiable cause.

§ To meet the ECG or rhythm monitoring criterion, a probable case must include at least one of 1) ST-segment or T-wave abnormalities; 2) Paroxysmal or sustained atrial, supraventricular, or ventricular arrhythmias; or 3) AV nodal conduction delays or intraventricular conduction defects.

Using either the original or the revised Lake Louise criteria.

https://www.sciencedirect.com/science/article/pii/S0735109718388430?via%3Dihubexternal icon.

** https://academic.oup.com/eurheartj/article/36/42/2921/2293375external icon.

^{††} Typically described as pain made worse by lying down, deep inspiration, or cough, and relieved by sitting up or leaning forward, although other types of chest pain might occur.

Reference: (Gargano et al 2021).

